11.4 Dosing schedule

IVIG/Placebo:

2g/kg IVIG/placebo over 5 days. This is approximately 0.4g/kg body weight per day but the daily dose should be rounded down to the nearest complete vial, with any remaining prescribed dose being

infused on the final day. IVIG/placebo dose is capped at 200g over the 5 days and sites should not infuse more than 1g/kg per day. Treatment should be started within 5 days of randomisation.

Sites should make sure to consult their local policy for IVIG infusions rates. Prior to infusing IVIG, sites should ensure patients are adequately hydrated, especially those with a risk factor for thrombosis, renal complications, and diabetes mellitus. All patients, particularly those who are considered high risk (previous Venous Thromboembolism (VTE), family history, or known pregnancy), should have a VTE risk assessment performed. During administration of the first infusion of trial treatment participants' vital signs must be monitored during and for 60 mins after infusion. For infusions 2-5, vital signs must be monitored during and for 20 minutes after infusion and relevant information recorded on the appropriate CRF. Participants must also be observed for any signs of anaphylaxis.

Non-IMP: Steroids

All patients will also receive methylprednisolone 1g daily intravenously for 5 days, followed by 1mg/kg of body (maximum dose 60mg) oral prednisolone daily for two weeks. This is followed by a reduction in 10mg per week until patient is taking 10mg daily, and then a further reduction in 1mg per week until stop. Minor variations in steroid dosing to due to participant's tolerance are allowed. All patients should have their blood sugar monitored while on steroids but those who are considered high risk (known diabetics, know pregnancy etc.) may require additional monitoring checks. In addition all patients will get a protein pump inhibitor (or similar alternative) to protect against gastric ulcers, and a calcium supplement and bisphosphate to protect against bone loss for the duration of steroid treatment. If adrenal deficiency is suspected, sites should follow standard local practice to manage the condition. It is recommended that all sites follow the NICE guidelines for steroids use during pregnancy. If sites have concerns regarding steroid regime or dose adjustments they should discuss with the site PI, and if necessary, they should contact the central trial team for guidance.

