The aim of the study is to test the effectiveness of early IVIG treatment on time to recovery for autoimmune encephalitis. This will be a multicentre double-blind two-arm placebo-controlled randomised superiority trial of IVIG in adults with autoimmune encephalitis, incorporating an internal pilot study. The patients, their families, health care workers and the study team will all be blinded to protect against performance and ascertainment bias. A total of 356 adult participants with a diagnosis of autoimmune encephalitis, will be randomised from 50 UK based secondary and tertiary care centres in a ratio of 1:1 to receive either IVIG (2g/kg over 5 days) or placebo treatment (0.9% Saline). All participants will also receive methylprednisolone 1g daily intravenously for 5 days, followed by 60mg oral prednisolone daily for two weeks, and then taper regime (see section 1.4 for full dosing schedule).

The total trial duration is 73 months and the end of trial will be defined as last participant, last visit. There will be an internal pilot study comprising of 50 participants and several stop/go decision points at study month 10 and then at 6, 12, 18, and 24 months recruitment. Data collected will comprise of clinical data, questionnaires, and samples. GOSE assessments will occur fortnightly for the first 3 months and then monthly till 12 months post randomisation. Clinical assessment will occur at 2 weeks, 3 months and 12 months post randomisation, and annually. Participants will be followed up post study completion through the use of data linkage via NHS digital. This will constitute a separate study and will be funded and reported separately..

Cerebrospinal fluid (CSF) and serum IgG Fc glycosylation will be measured at baseline for all patients and compared with CSF and serum samples from 40 controls - patients who had a lumbar puncture for non-inflammatory causes such as migraine and idiopathic intracranial hypertension. Serum IgG glycosylation samples will be taken again at 3 months.

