10.2 Lost to Follow Up

Sites will contact patients for each visit in accordance with the procedure outlined in section 13.2. If patients are not able to be contacted after three missed regular (fortnightly or monthly) GOSE assessment, a letter will be sent out to the participant asking them to get in contact with the trial team. Participants will not be contacted again until the 3 month, 12 month, or annual follow up occurs. Sites will record all details regarding attempts to contact the participant on the appropriate CRF. To minimise missing data, participants will be able to complete the primary outcome online or over the phone. In addition, contact details for participant's study partner will be collected and they will be able to complete the primary outcome on behalf of the participant. All data from participants will be collected regardless of their adherence to the protocol.

11 Trial Intervention

Patients will receive IVIG (2g/kg over 5 days) or placebo (Saline solution).

IVIG is a preparation of antibodies made from blood donations. It is licensed for use in patients with primary and secondary immunodeficiencies and for certain neurological conditions, such as Guillain-Barré syndrome. IVIG is given to many patients with autoimmune encephalitis. However, its efficacy is not known, and being a blood product, it carries risk of side effects.

We choose 2g/kg IVIG over 5 days (0.4g/kg/day for 5 days) because it is the dosing regimen most commonly used in neuro-inflammatory conditions, including in Guillain-Barré syndrome, and is the dose used in the pilot study of IVIG in encephalitis (Rayamajhi et al., 2015).

All patients will also receive methylprednisolone 1g daily intravenously for 5 days, followed by 1mg/kg (up to 60mg daily maximum) oral prednisolone daily for two weeks, followed by a taper regime (see section 11.4 for full dosing schedule).

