11.1 Treatment(s)

The trial is being carried out under a CTA. The drug is therefore only to be used by the named investigators, for the participants specified in this protocol, and within the trial. Sites may use any brands in accordance with local hospital policy. IVIG comes as a sterile clear, or slightly opalescent and colourless to pale yellow solution, which is isotonic, with an approximate osmolality of 320 mOsmol/kg. IVIG is licensed for use in the UK. Despite being commonly used to treat autoimmune encephalitis, it is not currently licensed for this use. IVIG comes in ready to use single use vials, containing 10g/100ml

solution which does not need to be diluted and contains human protein of which at least 98% IgG, trace amounts IgA (no more than 25 micrograms/ml), and is essentially sodium free. Other ingredients are amino acid proline and water. The responsibility for the safety profile, including screening for COVID-19, of the IVIg will lie solely with the manufacturers of the product.

The placebo is saline solution. The solution will contain 0.9% sodium chloride. The placebo will be bottled in matched 100ml single use vials. Placebo bottles should be stored below 30°C in all original packaging.

The current trial will use a Summary of Product Characteristics. Sites should ensure to consult the appropriate SmPC for clinical management decisions.

Patients will receive an infusion via IV of IVIG (2g/kg over 5 days) or placebo (saline solution). All patients will also receive methylprednisolone 1g daily intravenously for 5 days, followed by 1mg/kg of body weight, with a maximum dose of 60mg, oral prednisolone daily for two weeks. This will be followed by a taper regime (see section 11.4 for full dosing schedule).

For the first 14 days post randomisation, all other immunomodulatory treatment should be avoided. Once the 14-day period has elapsed, anti-neuronal antibody results will be reviewed and assessment on whether the patient has improved, stabilised or deteriorated will be made. If deemed necessary further non-IVIG treatment such as steroids, or plasma exchange will be considered. IVIG may be an option only after these alternatives have been considered. This procedure will be used in the event of subsequent deterioration or in the event the treating clinician determines additional treatment is necessary.

Figure 1 Treatment Schedule

Treatment	IVIG or	Methylprednisolone	oral	Recovery	Further Treatment
Day	Placebo		prednisolone	Assessment	

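### With the 10 g vial the protocol describes, the dose-rounding, final-day and daily-maximum rules in section 11.4 cannot all be met for participants above 40 kg and below 50 kg

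*Protocol*

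**What the plan says.** **Infusion.** Section 11.4 gives four instructions together:

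- a total of "2g/kg IVIG/placebo over 5 days";
- a nominal daily amount: "This is approximately 0.4g/kg body weight per day";
- a rounding rule: "the daily dose should be rounded down to the nearest complete vial, with any remaining prescribed dose being" carried to day 5;
- two limits, a 200 g cap on the course and a daily maximum: "sites should not infuse more than 1g/kg per day".

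Section 11.1 describes the product: "IVIG comes in ready to use single use vials, containing 10g/100ml" of solution, with placebo in matching 100 ml vials. Section 15.5 repeats the 10 g/100 ml size for the reference safety information. No other vial size appears, although section 11.1 lets sites use any brand under local policy. Sections 8.1 and 8.2 set no weight limit for entry.

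**Prednisolone.** Section 6 says "followed by 60mg oral prednisolone daily for two weeks". Section 11 says "followed by 1mg/kg (up to 60mg daily maximum) oral prednisolone daily for two weeks", and the synopsis, section 11.1, Figure 1 and section 11.4 also give 1 mg/kg with a 60 mg maximum. Section 6 sends the reader to section 1.4 for the schedule, which is in section 11.4. Figure 1 lists the full oral dose on days 6 to 20 and starts the taper on day 21.

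**The concern.** Rounding down on four days moves dose to the fifth. For some light adults the amount moved is large enough that day 5 exceeds the limit set in the next sentence. A site must then either exceed the daily maximum or give less than the prescribed total, and nothing says which instruction yields or what happens to an undelivered remainder. Section 11.12 requires dosing deviations to be recorded, so a site can follow one rule and still have to log a departure from another.

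The matter bears on safety because the dose is concentrated in the lightest participants. Section 11.4 itself asks for attention to thrombosis and renal risk, and section 11.7 names fluid overload, renal impairment and hyperviscosity as the things to watch for after an overdose.

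The prednisolone wording raises a smaller problem of the same kind: the daily amount for a participant under 60 kg depends on which section is read.

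**Working it through.** **Inputs.** Total 2 g/kg, nominal 0.4 g/kg per day, rounding down, remainder on day 5, 200 g cap and 1 g/kg daily maximum (section 11.4); vial size 10 g (sections 11.1 and 15.5).

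**The plan's own figure.** 2 g/kg ÷ 5 days = 0.4 g/kg per day. This reproduces.

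**The rule as written.** For weight w in kg:

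- days 1 to 4, each: 10 × floor(0.4w / 10) g
- day 5: min(2w, 200) − 4 × (that amount) g
- limit on day 5: w g

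From 25 kg to just under 50 kg, 0.4w lies between 10 and 20 g, so each of days 1 to 4 is 10 g. Day 5 is 2w − 40, and 2w − 40 > w whenever w > 40.

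| Weight (kg) | Prescribed total (g) | Days 1–4, each (g) | Day 5 (g) | Day 5 (g/kg) | Total if day 5 is held at 1 g/kg |
|---|---|---|---|---|---|
| 40 | 80 | 10 | 40 | 1.00 | 2.00 g/kg |
| 41 | 82 | 10 | 42 | 1.02 | 1.98 g/kg |
| 45 | 90 | 10 | 50 | 1.11 | 85 g = 1.89 g/kg |
| 49 | 98 | 10 | 58 | 1.18 | 89 g = 1.82 g/kg |
| 49.9 | 99.8 | 10 | 59.8 | 1.20 | 89.9 g = 1.80 g/kg |
| 50 | 100 | 20 | 20 | 0.40 | 2.00 g/kg |

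At 49 kg, day 5 carries 58/98 = 59% of the course.

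**Why only this band, and how it moves with vial size.** For a vial of v grams write 0.4w = kv + r, with k whole vials and 0 ≤ r < v. Below the 200 g cap, day 5 is 5(kv + r) − 4kv = kv + 5r, and the limit is w = 2.5kv + 2.5r. Day 5 exceeds the limit when 2.5r > 1.5kv, that is r > 0.6kv.

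- k = 0: exceeded for any r > 0, so for w below 2.5v.
- k = 1: exceeded when r > 0.6v, so for w above 4v and below 5v.
- k ≥ 2: never, because r would have to exceed 1.2v.

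| Vial | Weights in conflict, 25 to 150 kg |
|---|---|
| 5 g | none |
| 10 g | above 40 to below 50 kg |
| 20 g | 25 to below 50 kg, and above 80 to below 100 kg |

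A search from 25 to 150 kg in 0.1 kg steps, with the 200 g cap applied, gives the same bands.

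**Final day in whole vials.** The text does not say that the remainder is also rounded down. If it were, with 10 g vials, 44 kg would give 48 → 40 g on day 5, within the limit. At 45 kg it would be 50 g and at 49 kg 58 → 50 g, both above the limit. The conflict narrows to 45 to below 50 kg.

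**Prednisolone.** At 45 kg, section 6 gives 60 mg and section 11.4 gives 45 mg (ratio 60/45 = 1.33). At 50 kg the figures are 60 mg and 50 mg. From 60 kg upward they agree. Figure 1, days 6 to 20, is 20 − 6 + 1 = 15 full-dose days, against 14 in the text.

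**The case against.** Several points can fairly be made in the protocol's defence.

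- **Vial size.** Sites use hospital stock of any brand, and 5 g vials remove the conflict. This stands as a condition on the finding. It does not remove it, because 10 g is the only size the protocol names, the placebo is bottled to match, and a larger vial would widen the band.
- **Precedence.** The daily maximum shares a sentence with the 200 g cap, which plainly overrides 2 g/kg, so it may be meant to limit the remainder too. On that reading the shortfall is at most about 10% (1.80 g/kg at 49.9 kg). This is a possible reading, but the text neither states it nor says what becomes of the undelivered amount.
- **Whole vials on day 5.** Vials are single use, so whole-vial dosing on the last day is plausible. It narrows the band without closing it.
- **Number affected.** The protocol gives no weight distribution, so the share of the 356 participants cannot be stated.
- **Steroids.** Section 6 is an overview, every other place gives the weight-based dose, Figure 1 differs by one day, and both arms receive the same steroids. These items are minor. The allowance in section 11.4 for small variations due to tolerance does not reconcile a difference in the instruction itself.

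A reader might also infer that these participants would drop out of the efficacy population. The protocol does not support that. Section 16.7 defines that population by receipt of the allocated treatment and sets no dose threshold, and the weighting in section 17.1 addresses treatment switching and further immunotherapy. The primary analysis is by intention to treat, and the pilot adherence measure in section 14.1 is starting treatment within five days.

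**Conclusion.** The infusion instructions in section 11.4 contradict each other for participants above 40 kg and below 50 kg when 10 g vials are used. Day 5 reaches between just over 1.0 and 1.2 g/kg, or, if held at 1 g/kg, the course falls to between just under 2.0 and 1.8 g/kg. Such participants are eligible, and no rule says which instruction gives way.

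The result rests on the 10 g vial and on giving the exact remainder on day 5. It should not be read as saying that the rules conflict whatever stock a site holds. The number of participants affected is unknown, and no consequence for any analysis has been shown. This is an inconsistency in dosing text; the stated 0.4 g/kg figure is correct. It deserves correction because it bears on safety in light participants and costs little to settle.

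The prednisolone differences are real but minor: a different daily amount for participants under 60 kg in section 6, a wrong cross-reference there, and one extra full-dose day in Figure 1.

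**What to change.** The sponsor's clinical and pharmacy leads should reconcile the rounding, final-day and daily-maximum sentences in section 11.4 so that all can be met at every eligible weight and every vial size that sites may use. The text should say whether the final-day amount is given in whole vials, and what happens to any remainder that cannot be given. The pharmacy manual should carry the same wording. Section 6, Figure 1 and section 11.4 should be made to agree on the prednisolone dose and the number of full-dose days, and the cross-reference in section 6 corrected. Which rule or dose prevails is for the sponsor to decide.

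The cost is an amendment to protocol and pharmacy-manual wording and a notice to sites. Sample size, randomisation and the analysis are unaffected.

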11.5 Dose modification for toxicity

The list of expected reactions for IVIG can be found in the appropriate SmPC and treatment for them will depend on the nature of the reaction as well as local hospital practice. IMP/Placebo dose can be modified in the event of a toxicity but must be reported on the appropriate CRF. Any toxicities that meets the definition of an SAE (see section 15.2 and 15.3) must be reported within 24 hours of knowledge of the event according to the procedure outlined in section 15.6.

11.6 Management of toxicity and hypersensitivity reactions

If anaphylaxis should occur, IMP treatment must be stopped immediately. Staff administering the IMP must be trained in acute management of anaphylaxis reactions and this must include the administration of intra-muscular adrenaline and be specified on the delegation log. Adrenaline must be available during administration and should be prescribed on the participant's drug chart prior to administration of IMP.

11.7 Management of overdose

If an overdose is suspected, site staff should monitor for fluid overload, renal impairment and hyperviscosity. Sites should notify the trial manager by emailing [contact] in all cases of suspected overdoses. If the overdose causes an event that meets the criteria of an SAE (see section 15.2) it must be reported as an SAE according to the procedures outline in section 15.6.

11.8 Pre-medication

There are no pre-medication requirements

11.9 Prohibited medications and interaction with other drugs

During the first 14 days post randomisation, the use of additional immunomodulatory treatment will not be allowed. Once this period has elapsed, and it is determined the patient requires further treatment, non-IVIG treatment such as steroids or plasma exchange must be first considered. If after other treatment options have been considered, clinicians may administer IVIG if appropriate.

Clinician should avoid administering loop diuretics. If immunomodulatory treatment is administered within the initial 14 day window, the central trial team must be notified immediately and the appropriate CRF completed as soon as possible.

IVIG:

IVIG can impair the effectiveness of live attenuated virus vaccinations for up to 3 months. In the case of the measles vaccination, it can reduce the effectiveness for up to a year. It is recommended to wait for at least 3 months after IVIG treatment prior to having a live attenuated virus vaccination. In the case of patients receiving the measles vaccination, it is recommended they have their antibody status checked. Full details can be found in the SmPC.

Steroids:

For information relating to contraindications, trial staff should consult their specific SmPC.

11.10 Permitted concomitant medications and additional clinical procedures

All other medications are permitted except those listed in 11.10.1 trial restriction of the protocol and any medication listed in the appropriate SmPC.

Sites should monitor for complications arising from any lumbar punctures and manage them according to standard local practice.

11.10.1 Trial restrictions

Patients on Dinutuximab should not be prescribed immunoglobulins.

11.11 Accountability procedures

All accountability procedures will be outlined in the trial specific pharmacy manual and IMP management plan. Local pharmacies will be asked to log vial numbers, batch number, expiry date, date drug was dispensed, initials of trial member who requested drug, and returns. All bottles, even if empty, must be returned to the pharmacy. Upon return of any IMP/Placebo bottles, the pharmacy will confirm receipt of bottle and confirm that the packaging was not tampered with. To dispose of the drug, the pharmacy will contact the central trial team who will then issue a letter confirming permission to destroy trial stock. Destruction date will be recorded on the accountability log. In the event that the IMP was not administered according the outlined schedule (see section 10.4), the reason must be documented in the appropriate CRF.

11.12 Compliance

Any deviations from dosing schedule outlined in the trial protocol will be recorded on the appropriate CRF and will include at minimum new dose given, and reason for dose adjustment.

12 Sample Management

Participants will be asked if they are willing to consent to provide blood and/or CSF samples for the exploratory sub-studies. These samples will be used to explore the mechanisms by which IVIG produces benefit in patients. No samples collected for research (i.e. the exploratory sub-studies) will be used to inform primary or secondary trial outcome measures. The research samples (extra volumes of blood and/or CSF) will be collected at baseline (prior to IVIG treatment), 2 weeks and 3 months.

Samples will aim to be collected when the patient undergoes venepuncture / lumbar puncture as part of their clinical care at these time-points in their illness (to minimise unnecessary extra procedures).

As part of the consent process participants will be also be asked if any left-over CSF / blood remaining in the hospital laboratory after their initial clinical investigations (to determine if the patient had encephalitis) can be 'salvaged' and used to support the exploratory studies. These samples will particularly inform exploratory measurements for the 'acute' time-point of hospital admission. Local hospital laboratories will be informed of all participants who have consented for salvaged samples to be stored for the exploratory sub-studies.

Research samples (collected and salvaged) will initially be stored at hospital site in accordance with local policy. They will then be transported in batches to the University College London (UCL) Neuroimmunology and CSF Laboratory for central storage. Once received and logged by the lab at the University College London, samples will undergo exploratory measurements of inflammatory/host response markers (including glycosylation studies), and host biomarkers of brain damage at UCL. Some samples may also be transferred to the lab in University of Oxford to undertake detection / measurement for novel auto-antibodies. At the end of the trial, if consent is received samples will be sent to the University of Liverpool Ronald Ross building for storage in their biobank.

Figure 2 Sample Schedule and Quantities

Time	Acute	Baseline	2 weeks	3 months
CSF	5ml split into		4ml split into	
	4x1000μl and 2x500μl aliquots		3x1000μl and 2x500μl	
	1.proteome		aliquots	
	100μΙ		1.proteome	
	2.cytokines		100μΙ	
	1000μΙ		2.cytokines	
	3. Brain Damage Markers		1000μΙ	
	(e.g. neuro-filaments (NFL), Tau, S100B, 14-3-3)		3. Damage Markers	
	1000μΙ		(e.g. NFL, Tau, S100B, 14-3-3)	
	4.OCB,IgG,IgM,Albumin		1000μΙ	
	1000μΙ		4.OCB,lgG,lgM,Albumin	
	5. Host (+/-virus) Seq		1000μΙ	
	500μΙ		5. Host (+/-virus) Seq	
			500µl	
CSF	ONLY local sites to Oxford:			
	6. CSF Cell separation: 1000μl			
Blood		1. Serum – BD Vacutainer SST 8.5ml	1. Serum – BD Vacutainer SST	1. Serum – BD Vacutainer
		[red/grey marble top] tube.	8.5ml [red/grey marble top]	SST 8.5ml [red/grey marble
		[This tube will collect 3.5ml of serum.	tube.	top] tube.
		Following venepuncture invert 5 times	a.lgG glycosylation	a.lgG glycosylation
		to mix. Rest for at least 30 mins	100μΙ	100μΙ
		(ideally 2 hrs) for clot activation.	b. damage markers	b. damage markers
		Centrifuge 2000g 10min (or 3000g	1000μΙ	1000μΙ
		5min) within 48hrs. Then aliquot	c. cytokines -	c. cytokines -
		serum into 7x500ul aliquots and	1000μΙ	1000μΙ
		freeze -80°C]	d. proteome	d. proteome
		a.lgG glycosylation	400μΙ	400μΙ
		100μΙ	e. Albumin, OCB, IgG,IgM	e. Albumin, OCB, IgG,IgM
		b. brain damage markers	1000μΙ	1000μΙ
		1000μΙ		

Time	Acute	Baseline	2 weeks	3 months
		c. cytokines -		
		1000μΙ		
		d. proteome		
		400µl		
		e. Albumin, Oligo-Clonal Bands (OCB),		
		lgG,lgM		
		1000μΙ		
		2. RNA stabilized – 2.5ml	2. RNA stabilized – 2.5ml	2. RNA stabilized – 2.5ml
		Host transcripts	Host transcripts	Host transcripts
		3. BD Vacutainer EDTA [lilac top] – 3ml		
		Host DNA/		
		HLA sequencing		
		4. BD Vacutainer Sodium Heparin		
		10ml [green-top] tube: -		
		Whole blood-PBMC		
		Separation		
		Plasma-AutoAb		
		(ONLY local sites to Oxford)		

Any baseline samples should be taken prior to starting treatment. Given that some samples will be obtained from samples taken as part of routine care and that it may not be possible to obtain the necessary volume of blood or CSF, the samples should be collected in the order of importance and prepared in the manner specified below and:

For CSF Samples:

CSF must be taken in polypropylene tubes (can then be decanted / aliquoted into cryovial tubes at the local laboratory for ease of storage): draw 5mls

Laboratory Processes: Labs will be asked to "Freeze and Phone" any CSF from screened participants that is sent for analysis and is not used for clinical reasons (spare CSF). Any spare CSF will be ring fenced until consent is confirmed. Once consent for use of the sample is confirmed that lab will process and aliquot the sample. If consent is not confirmed, the sample will be destroyed.

If there is no spare CSF available following lumbar puncture (LP) at screening this will not preclude entry to the RCT. Sites are asked to phone in all instances. Where patients undertake a follow-up LP we request an additional volume of CSF is collected during the LP for research purposes.

For Blood Samples:

- a. Blood in PAXgene tubes: 2.5mls
 - Filled Blood collection tubes should initially be gently mixed by inverting five times, then rested at ambient temperature for 2 hours. Tubes should then be frozen at -80°C (an initial period (up to 1 month) at -20°C is acceptable)
- b. Blood in BD Vacutainer Serum Separator Tubes (SST): 8.5mls
 Filled Blood collection tubes should initially be gently mixed by inverting five times, then rested at ambient temperature for 2 hours. Next, they should be centrifuged at 2000g 10min (or 3000g 5min) within 48hrs. The resulting serum should then be aliquoted into 7x500ul aliquots and frozen at -80°C
- c. Blood in BD Vacutainer EDTA tube: 3mls
 - Filled Blood collection tubes should initially be gently mixed by inverting five times, then rested at ambient temperature for 2 hours. Tubes should then be frozen (-80°C).
- d. Blood in BD Vacutainer Sodium Heparin tube: 10mls (ONLY at sites local to Oxford/Liverpool) Sodium Heparin tubes should only be collected at hospital sites local to Liverpool or Oxford. The tubes need to be transported within 24 hours of collection and arrive at the University (Liverpool or Oxford) on a Monday-Thursday 9-5pm. During

collection/transportation the tubes should be kept at ambient temperature. Tubes can be sent via NHS courier systems (e.g. DX) established at the participating sites. The tubes will be processed at the relevant University

The coordinating centre will provide sample packs for sites to use. The location of these packs will be in the site file. Locally sourced tubes can also be used. If additional sample packs are required, sites should email [contact].

